3.6. Data source

Patients will be identified from a multicenter, multinational LT patient database, which is being developed at the University of Toronto, Canada. This new database will contain retrospective patient-level data from several lung transplant centers in the EU, North America and Australia that agree to contribute patient-level data to the database under development.

A recently completed site feasibility assessment by the PI showed that some transplant centers use 'complete electronic medical records' (EMR) i.e., maintaining all medical records such as medication use, diagnosis, pathology reports in both inpatient and outpatient settings in EMR, some use 'partial EMR', i.e., some data in EMR and others in paper-based records, and some use 'paper records only' i.e., maintaining all data in paper charts only. Of the 19 transplant centers contacted by the PI, 16 completed the site feasibility assessment questionnaire. Of these 16 centers, six centers have complete EMR (four in EU and two in North America), eight centers have paper records only. The feasibility assessment data suggest that it is feasible to conduct a retrospective cohort study with an adequate power in transplant centers that either have complete EMR or have partial EMR. To minimize the time needed to compile the new database, the study will mainly target the centers with complete EMR. Centers with partial EMR will be enrolled if needed to ensure enough number of LT patients is included in the database.

As of 10 February 2011, three centers in North America have been enrolled in the study (two with complete EMR and one with partial EMR data). The PI is in the process of enrolling additional centers who have expressed interest to participate in the study. These centers are based in Germany (1 center), Italy (1), Belgium (1), UK (1), Switzerland (2), Spain (2), US (2), and Australia (1).

3.7. Patient selection

Consecutive eligible patients undergoing LT at the study transplant centers between 1 January, 2005 and 31 December, 2008 will be included. An attempt will be made to collect post transplant follow up data for all surviving patients until the end 2012.

3.8. Sample size and power

Appendix 1 describes the sample size estimations of a retrospective cohort study addressing the study primary objective based on different assumptions. Assuming a p_0 value (i.e., incidence of SCC of skin in LT patients unexposed to voriconazole) of 5% and voriconazole exposed-tounexposed ratio of 1:2, the study would require at least 157 patients in the voriconazole exposed cohort and 314 patients in the unexposed exposed cohort to detect a relative risk (RR) of 2.5 with 80% power at a 5% significance level.

3.9. Data collection

The data will be abstracted from EMR at centers with complete EMR. At transplant centers with partial EMR, the data elements in EMR will be linked to data in paper records using a "patient medical record number." Extracted data from each center will be compiled in the study database. The study database will only contain the encrypted identification of the patients and will be protected by a firewall and a password. The following data will be collected.

3.9.1. Voriconazole and other antifungal treatment

Data on voriconazole therapy will include:

- Indication:
 - o Prophylaxis of IFIs
 - o Treatment of IFIs
- Dose and frequency
- Duration of therapy (will be calculated by using the treatment start and stop dates)

Data on antifungl agents other than voricoanzole (e.g., itraconazole, posaconazole, amphotericin B) will also be collected.

3.9.2. Outcomes

Data on the diagnosis of SCC of skin and melanoma will be obtained from the medical records. Information on the biopsy report confirming the diagnosis will also be collected, when available. In addition, data on other serious skin related events, including phototoxicity will be collected.

3.9.3. Risk factors and potential confounders for SCC of skin

The following data will be collected:

- Age
- Gender
- Race/ethnicity
- Occupation
- Skin phototype
- Geographical location of residence (surrogate for sun exposure)

- History of immune disorder or malignancy prior to transplant.
- Type of transplant (lung vs. heart-lung, single vs. double lung, re-transplant)
- Cytomegalovirus (CMV) serostatus (donor and recipient)
- Reason for transplant (chronic obstructive pulmonary disease (COPD), cystic fibrosis, other)
- Days in intensive care unit (ICU), days in hospital at the time of transplant, need for readmission
- Need for hemodialysis during transplant admission
- Number of transplant rejection episodes
- Number of episodes of neutropenia after transplant
- Use of immunosuppressive agents after transplant
 - Interleukin (IL)-2 inhibitors (i.e., basiliximab, daclizumab, alemtuzumab).
 - Alemtuzumab (Campath)
 - Thymoglobulin
 - Calcineurin inhibitors (CNIs) (tacrolimus, cyclosporine) with number of episodes with elevated levels
 - Sirolimus, everolimus
 - Mycophenolate
 - Corticosteroids
- Use of phototoxic agents after transplant
- Presence or absence of phototoxicity after the LT as documented in medical records
- History of SCC

3.9.4. Quality control

Data collected will be periodically checked for consistency by the study coordinator. The study investigators will follow their own Standard Operating Procedures (SOPs) for data collection and management.

4. ADVERSE EVENT REPORTING

This study protocol requires review of the patient medical chart and/or a narrative field in the dataset. Review of patient medical charts and narratives for specific attribution of SAEs to Pfizer drugs will not be actively pursued. However, while the primary purpose of this study does not encompass assessment of drug-related effects in individuals, the reviewer may identify an SAE with explicit attribution to a Pfizer drug via patient chart and/or narrative review (and with an identifiable reporter). Such SAEs must be reported to Pfizer or its representative for submission to regulatory authorities. Explicit attribution is not inferred by a temporal relationship between drug administration and an SAE but must be based on a definite statement of causality by a healthcare provider linking drug administration to the SAE.

A serious adverse event (SAE) is defined as any untoward medical occurrence that at any dose:

results in death;

- is life-threatening (i.e., at immediate risk of death due to the event);
- requires inpatient hospitalization or prolongation of existing hospitalization;
- results in persistent or significant disability/incapacity; or
- is a congenital anomaly/birth defect.

Medical and scientific judgment is exercised in determining whether an event is an important medical event. An important medical event many not be immediately life-threatening and/or result in death or hospitalization. However, if it is determined that the event may jeopardize the patient or may require intervention to prevent one of the other outcomes listed in the definition above, the important medical event should be reported as serious.

Examples of such events are intensive treatment in an emergency room or at home for allergic bronchospasm, blood dyscrasias or convulsions that do not result in hospitalization, or development of drug dependency or drug abuse.

If there is a written notation in the medical chart/narrative field indicating that a physician attributed a serious adverse event to a Pfizer drug, the abstractor will complete an SAE form within 24 hours of identification of the event and submit it to Pfizer Safety. Since patients are de-identified, such information will not include any patient or physician identifying information such as name, address, or phone number.

5. ETHICAL CONSIDERATIONS

This study will be conducted in accordance with legal and regulatory requirements, as well as with scientific purpose, value and rigor and follow generally accepted research practices such as *Good Pharmacoepidemiology Practices* (GPP) issued by the International Society for Pharmacoepidemiology (ISPE), the International Society for Pharmacoeconomics and Outcomes Research (ISPOR) guidances, Pharmaceutical Research and Manufacturers Association (PhRMA) guidelines and similar.

5.1. Institutional Review Board (IRB)/Ethics Committee (EC) Approval

Ethics approval from each study center's IRB/EC will be sought before implementing the study at each center.

5.2. Confidentiality of the data

Confidentiality of the data will be maintained at all times. The database will only contain the encrypted identification of the patients. The database will be protected by a firewall, and stored in a password protected computer. All analyses will be conducted on appropriately de-identified data and reported only in aggregate form.

5.3. Informed consent

This study will utilize retrospective (i.e., existing data from medical charts) unidentified data after appropriate IRB/EC approvals. Therefore, informed consent from each patient is not required in this study.

6. DATA MANAGEMENT

There will be one final analytic dataset containing data from all study transplant centers. The final dataset will be maintained at the principal study center in secure servers that transmit information only over encrypted connections. Access to raw data bypassing record level protection will be given only to the PI, study coordinator and database administrator. For analyses, de-identified data will be used and kept in a password protected computer with limited physical access.

6.1. Missing values

There will be no imputation of missing values. All variables will include a category for missing values, where applicable.

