1. INTRODUCTION

Voriconazole (Vfend[®]) is approved for the treatment of invasive aspergillosis (IA) and other systemic fungal infections. In addition to the approved indications, published reports indicate that voriconazole is used as prophylaxis to prevent IA in solid organ transplant (SOT), primarily lung or lung/heart transplantation (LT) [1, 2].

Patients undergoing LT typically receive immunosuppressive medications for a period of time after the transplantation to prevent organ rejection. This prolonged immunosuppression renders these patients highly susceptible to invasive fungal infections (IFIs) such as IA [3]. As a result, antifungal prophylaxis is commonly prescribed for patients after LT in many transplant centers worldwide. Some transplant centers prefer universal antifungal prophylaxis for all patients, while others use "targeted" prophylaxis in only the highest risk patients. The data from a recent worldwide survey showed that voriconazole is the preferred antifungal for prophylaxis either as monotherapy or in combination with another antifungal agent[4]. It is important to note, however, that there have been no prospective comparative clinical trials conducted to evaluate the safety and efficacy of voriconazole prophylaxis in this clinical situation, and voriconazole has not been approved by any regulatory authority for this use.

Squamous cell carcinomas (SCC) is the second most common skin cancer in the general population after the basal cell carcinoma (BCC), and it is the most common cancer in immunocompromised patients with SOT. Overall, the incidence of SCC in SOT patients is 65 to 250 times that of the general population [5], and varies by type of organ transplant. Furthermore, SCC has been reported to be more aggressive and has been associated with a high mortality in immunocompromised patients [6]. The recognized risk factors for the development of SCC include old age, prolonged sunlight exposure, long duration of immunosuppressive therapy, infection with human papillomavirus (HPV) and lower CD4 cell counts, and certain host factors such as White race and Fitzpatrick skin types I, II, or III [7-9].

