7.3.1. Analyses to address primary objective

Comparison of voriconazole exposed cohort and unexposed cohort: A univariate Cox proportional hazard regression analysis will be conducted to assess the association between voriconazole and SCC of skin. Based on the results of the univariate analysis, a multivariate Cox proportional hazard regression model will be developed to evaluate the independent effect of voriconazole use on the risk of SCC of skin while controlling for effects of major confounding variables such as exposure to sunlight (using geographical location of residence as a proxy variable), immune status (using immunosuppressive medications as a proxy variable) and confounding by indication (using underlying medical conditions as a proxy variable). In addition to multivariate regression analyses, other analytic methods will be considered in order to control for major confounders such as patients' immune status and exposure to sunlight.

Further, depending on the number of patients, subgroup analyses such as comparison of patients who receive voriconazole but no other antifungals (i.e., 'voriconazole only cohort') with patients who did not receive voriconazole (i.e., unexposed cohort) will be considered to assess the association between voriconazole and SCC of skin.

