- **Confounding by indication:** Confounding by indication is likely to take place in this study if a physician's decision to initiate a particular antifungal (s) for prophylaxis is influenced by the clinical status of the patient. This is of particular concern for voriconazole, which is a preferred antifungal agent in many transplant centers, as physicians are more likely to use voriconazole if patients are severely ill or are at high risk of acquiring IFIs. This could result in an association of voriconazole use with untoward outcomes including SCC of skin or melanoma. Although complete control of confounding by indication may not be possible, data on co-morbid conditions and laboratory tests will be collected and used in the statistical analyses (i.e., multivariate regression) for controlling its confounding effect.
- Generalizibility of study findings to voriconazole treated patients overall: It should be noted that the findings from such a study may not be generalizable to all voriconazole-treated patients with regards to the risk of SCC of skin as patients with LT are a special patient population with unique factors that make them more susceptible to SCC of skin.

- **Confounding by study center:** This study will include data from several transplant centers in the EU, North America and Australia. Therefore, factors such as sun exposure levels, and management and treatment of patients with LT will vary by study centers. The potential confounding effect by study center will be accounted for in the statistical analyses.
- **Misclassification of exposure:** The data on medication use more than three months prior to the transplant may not be available for most patients. which may result in misclassification of exposure. However, since the majority of patients receive antifungals at the time of transplant, the proportion of patients who may have received antifungal(s) three months before LT would be very small.
- **Exposure to sunlight:** Patients' exposure to sunlight has been identified as a risk factor for the SCC of skin. Exposure to sunlight or use of sun protective measures is not routinely documented in medical charts for all patients with LT. A proxy variable based on a patient's area of residence (e.g., highly exposed to sunlight versus not) will be developed and used in the analyses in the absence of individual-level data on exposure to sunlight.

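### Section 6.1 bars imputation in favour of a missing category, which pulls the adjusted voriconazole hazard ratio towards the crude one when an incomplete confounder differs between cohorts

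*Protocol*

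**What the plan says.** Section 6.1 states: "There will be no imputation of missing values. All variables will include a category for missing values, where applicable". The protocol plans no sensitivity analysis for missing covariates. Section 7 refers to a SAP for detail, which was not available for this check, but the rule itself is set in the protocol.

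Other sections bear on it:

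- **Source of covariates.** Section 5.3: "This study will utilize retrospective (i.e., existing data from medical charts) unidentified data". Section 3.6 allows centres whose records are partly on paper.
- **Risk factors.** Section 1 lists among the recognised risk factors for squamous cell carcinoma (SCC) "certain host factors such as White race and Fitzpatrick skin types I, II, or III". Section 3.9.3 collects "Skin phototype", race/ethnicity, occupation, immunosuppressive agents, rejection episodes and neutropenia episodes.
- **Primary analysis.** Section 7.3.1 plans a multivariate Cox model "controlling for effects of major confounding variables such as exposure to sunlight", immune status and confounding by indication, each through a proxy.
- **Sunlight.** Section 8: "Exposure to sunlight or use of sun protective measures is not routinely documented in medical charts for all patients with LT". A proxy based on area of residence "will be developed and used in the analyses in the absence of individual-level data on exposure to sunlight".
- **Centre.** Section 8: "The potential confounding effect by study center will be accounted for in the statistical analyses". The method is not given.

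**The concern.** A missing category puts all patients with an unrecorded confounder into one stratum. Within it, exposed and unexposed patients still differ on the unrecorded variable, so the voriconazole effect there is the crude effect with respect to that variable. The Cox model pools this stratum with the properly adjusted ones, and the result lies between the adjusted and the crude estimate. This needs no informative missingness; an imbalance between cohorts is enough.

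Section 1 criticises two earlier studies for inadequate control of immune status, and section 8 lists control of confounding as a strength of this one. The rule in 6.1 covers immune-status covariates as well as phototype and race. It can therefore weaken the control the study was designed to provide, with no planned analysis that would show it.

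**Working it through.** **1. The plan's own figure, for scale.** Section 3.8 takes an unexposed risk of 5%, relative risk 2.5 (exposed risk 12.5%), ratio 1:2, two-sided 5% and 80% power. The pooled risk is (0.125 + 2 × 0.05)/3 = 0.075.

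n exposed = [1.960 × √(1.5 × 0.075 × 0.925) + 0.8416 × √(0.125 × 0.875 + 0.05 × 0.95/2)]² / 0.075² = (0.6323 + 0.3071)² / 0.005625 = 156.9

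This rounds up to 157 exposed and 314 unexposed, as stated. The present point does not affect that sample size.

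**2. Inputs for the bias.** From the protocol: the 1:2 ratio and the missing-category rule. Assumed, because the protocol gives no figures: one binary confounder with relative risk R = 3, prevalence p1 in the exposed and p0 in the unexposed, a true voriconazole relative risk of 1.0, and a fraction m missing completely at random. There are no other covariates. A log-linear risk model stands in for the Cox model, and the baseline risk cancels.

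**3. Effect inside the missing stratum.** It equals the crude relative risk, [1 + p1(R − 1)] / [1 + p0(R − 1)]:

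- 70% vs 60%: 2.4/2.2 = 1.09
- 80% vs 60%: 2.6/2.2 = 1.18
- 65% vs 35%: 2.3/1.7 = 1.35
- equal prevalence: 1.00

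**4. Pooled estimate.** In large samples the adjusted relative risk θ solves

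Σ D_s × n1_s θ / (n1_s θ + n0_s) = total exposed events,

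summed over the strata confounder absent, confounder present and missing. Here n1_s and n0_s are the exposed and unexposed numbers and D_s the events, in units of the baseline risk.

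Example: 100 exposed, 200 unexposed, prevalence 80% vs 60%, 50% missing.

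| Stratum | Exposed | Unexposed | Exposed events | Unexposed events |
|---|---|---|---|---|
| Absent | 10 | 40 | 10 | 40 |
| Present | 40 | 60 | 120 | 180 |
| Missing | 50 | 100 | 130 | 220 |

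The equation is 50 × 10θ/(10θ + 40) + 300 × 40θ/(40θ + 60) + 350 × 50θ/(50θ + 100) = 260. Its solution is θ = 1.087, with terms 10.69 + 126.06 + 123.25 = 260.

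**5. Results, true relative risk 1.0.**

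| Prevalence exposed vs unexposed | Crude | 10% missing | 30% missing | 50% missing |
|---|---|---|---|---|
| Balanced | 1.00 | 1.00 | 1.00 | 1.00 |
| 70% vs 60% | 1.09 | 1.01 | 1.03 | 1.04 |
| 80% vs 60% | 1.18 | 1.02 | 1.05 | 1.09 |
| 65% vs 35% | 1.35 | 1.03 | 1.10 | 1.17 |

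At 70% missing the last row reaches 1.24.

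**6. Comparison.** In these scenarios a complete-case fit is unbiased: both observed strata have relative risk 1.0 (10/10 against 40/40, and 120/40 against 180/60, in the example). The bias comes from how the missing stratum is treated, not from the loss of data.

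**The case against.** The strongest objection is that the protocol shows neither ingredient of the bias: it gives no missingness rate and no imbalance. Section 8 links prescribing to illness severity and infection risk, not to skin type. If phototype or race is tied to voriconazole use mainly through centre, the promised centre adjustment recovers some of the control, as would residence and other recorded covariates. The calculation has one confounder and nothing else in the model, so it shows the loss before any such recovery. With modest imbalance the bias is 1% to 4%, small against the design relative risk of 2.5. Even if the null estimate drifted to 1.2, the two-sided rejection rate at 157 and 314 patients would be only about 7%. All of this stands, and it limits the size of the point. It does not remove the mechanism.

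A reader might infer three stronger things that the protocol does not support:

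- **That undocumented sun exposure is left unadjusted.** Sections 7.3.1 and 8 use residence in place of individual sun data, so a patient enters a missing category for sunlight only if residence is missing too.
- **That every variable gets a missing category.** Section 6.1 limits this to where it applies.
- **That affected patients are wholly uncontrolled.** They are not adjusted for the missing variable itself, but centre and correlated covariates may carry part of it.

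It is also fair to say that imputation is no cure-all. If phototype is charted selectively, or never at some centres, missing at random may fail.

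**Conclusion.** The point holds as a weakness in a rule the protocol itself fixes. Where an incomplete confounder is imbalanced between cohorts, the missing category biases the adjusted voriconazole hazard ratio towards the crude one, even under missing completely at random. The direction follows the imbalance: upward in the scenarios shown, downward if the risk factor is commoner in the unexposed.

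The size rests wholly on assumptions. For one binary confounder of relative risk 3 and no true effect, it runs from nothing (balanced), through 1% to 4% (70% vs 60%) and 2% to 9% (80% vs 60%), to 3% to 17% (65% vs 35%), each over 10% to 50% missing. Without missingness or imbalance figures, this should be fixed, but there is no ground for saying that it invalidates the primary analysis.

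**What to change.** Amend section 6.1 so that the primary adjusted Cox analysis uses multiple imputation of incomplete baseline confounders. The imputation model should contain voriconazole exposure, the event indicator, the cumulative hazard, centre and the other covariates. Outcomes and voriconazole dates should not be imputed.

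Keep complete-case and missing-category analyses as sensitivity analyses, and report the missing share of each variable by cohort and centre. Because this imputation covers baseline variables only, 6.1 should also say how incomplete post-transplant covariates, such as rejection or neutropenia episodes, are handled.

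The cost is a wording change and modest extra analysis, with no new data collection. The price is reliance on missing at random given the recorded data. That may fail if phototype is charted selectively or is never recorded at a centre, which is why the sensitivity analyses are needed. If missingness turns out to be low, the analyses will agree and little is lost.
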